3.3.2. Benefit Assessment

The primary data supporting efficacy of intravenous (IV) belimumab were the Phase 3 trials (C1056 and C1057) in which 1684 subjects were treated for up to 52 weeks (C1057) or 76 weeks (C1056) (Belimumab Investigator's Brochure, Section 5.3.1.2). Belimumab produced significant improvements in the SLE Responder Index as well as in the individual component Safety of Estrogen in Lupus National Assessment Trial (SELENA)-Systemic Lupus Erythematosus Disease Activity Index (SLEDAI) score in both studies. Pooled analyses demonstrated steroid sparing and decreased risk of severe flares over 52 weeks. Clinical trial data for belimumab since approval continue to show efficacy in the treatment of SLE through decreased SLE flares and decreased disease activity across multiple organ systems (Belimumab Investigator's Brochure, Section 5.3.1.3). Similar results were observed in the pivotal Phase 3 trial of belimumab SC 200 mg/week (BEL112341), with significant improvements in the SLE Responder Index and time to first severe flare endpoints. The inclusion of rituximab provides an opportunity for subjects with active SLE despite standard lupus therapy to benefit from potentially disease modifying regimen that may include induction of disease control or clinical remission and a reduction in or complete discontinuation of corticosteroids and immunosuppressant therapy.

3.3.3. Overall Benefit: Risk Conclusion

Taking into account the measures that will be implemented to minimize risk to subjects participating in this study, the potential risks associated with co-administration of belimumab and rituximab are justified by the anticipated benefits that may be afforded to patients with SLE who choose to participate in this trial.

4. OBJECTIVES AND ENDPOINTS

The key evaluations are based on comparing belimumab with or without a single cycle of rituximab (the combination arm vs. the control arm). There are limited analyses planned to compare the combination of belimumab with a single cycle of rituximab (combination arm) to belimumab with standard therapy (reference arm). Details of the analyses to be conducted will be described in the Reporting and Analysis Plan (RAP), including analysis of the combination arm vs. the control arm and the combination arm vs. the reference arm.

Objectives	Endpoints
Primary: Efficacy	
To evaluate the efficacy of belimumab and a single cycle of rituximab administered in a combination regimen to adult participants with SLE.	 Proportion of participants with a state of disease control defined as a SLEDAI- 2K score ≤2, achieved without immunosuppressants and with corticosteroids at a prednisone equivalent dose of ≤5mg/day at Week 52. (Serological activity, i.e., anti-dsDNA positivity and/or

Objectives	Endpoints
	hypocomplementemia, is scored in the SLEDAI-2K endpoint.)
Secondary: Efficacy (Major)	Proportion of participants with a state of clinical remission defined as a Clinical SLEDAI-2K score =0, achieved without immunosuppressants and with corticosteroids at a prednisone equivalent dose of 0 mg/day at Week 64. (Serological activity score, i.e., anti-dsDNA positivity and/or hypocomplementemia, is excluded from the Clinical SLEDAI-2K endpoint.)
	Proportion of participants with a state of disease control defined as a SLEDAI-2K score ≤2, achieved without immunosuppressants and with corticosteroids at a prednisone equivalent dose of ≤5 mg/day at Week 104.
Secondary: Efficacy (Other)	Proportion of participants with a state of disease control, defined as a SLEDAI-2K score ≤2, achieved without immunosuppressants and with corticosteroids at a prednisone equivalent dose of ≤5 mg/day, by visit.
	Proportion of participants with a state of clinical remission, defined as a Clinical SLEDAI-2K score =0, achieved without immunosuppressants and with corticosteroids at a prednisone equivalent dose of 0 mg/day, by visit. (Serological activity score, i.e., anti-dsDNA positivity and/or hypocomplementemia, is excluded from the Clinical SLEDAI-2K endpoint.)
	Proportion of participants with a state of complete remission, defined as SLEDAI-2K=0, achieved without immunosuppressants and with corticosteroids at a prednisone equivalent dose of 0 mg/day, sustained for at least 24 weeks.
	Proportion of participants with a state of clinical remission at Week 104, defined as

Objectives	Endpoints
	Clinical SLEDAI-2K score=0, achieved without immunosuppressants and with corticosteroids at a prednisone equivalent dose of 0 mg/day, sustained for at least 24 weeks. (Serological activity score, i.e., antidsDNA positivity and/or hypocomplementemia, is excluded from the Clinical SLEDAI-2K endpoint.)
	Proportion of participants with a state of complete remission, defined as a SLEDAI-2K score =0, achieved without immunosuppressants and with corticosteroids at a prednisone equivalent dose of 0 mg/day, by visit
	Time to first severe flare (as measured by the modified SLE Flare Index)
	Time to first flare (as measured by the modified SLE Flare Index)
	Time to disease control sustained to Week 104, defined as SLEDAI-2K score ≤2, achieved without immunosuppressants and with corticosteroids at a prednisone equivalent dose of ≤5 mg/day
	Time to clinical remission sustained to Week 104, defined as Clinical SLEDAI-2K score =0, achieved without immunosuppressants and with corticosteroids at a prednisone equivalent dose of 0 mg/day. (Serological activity, i.e., anti-dsDNA positivity and/or hypocomplementemia, is excluded from the Clinical SLEDAI-2K endpoint.)
	Duration of disease control, defined as SLEDAI-2K score ≤2, achieved without immunosuppressants and with corticosteroids at a prednisone equivalent dose of ≤5 mg/day
	Duration of clinical remission, defined as Clinical SLEDAI-2K score =0, achieved

Objectives	Endpoints
	without immunosuppressants and with corticosteroids at a prednisone equivalent dose of 0 mg/day. (Serological activity, i.e., anti-dsDNA positivity and/or hypocomplementemia, is excluded from the Clinical SLEDAI-2K endpoint.)
	Change from baseline in SLEDAI-2K score by visit
	Proportion of participants with SLEDAI-2K organ improvement by visit
	Proportion of participants with SLEDAI-2K organ worsening by visit
	Change from baseline in Physician Global Assessment (PGA) by visit
	Proportion of participants with any SLICC Damage Index worsening (change >0) compared with baseline at Week 52 and Week 104
	 Proportion of participants that meet the Lupus Low Disease Activity State (LLDAS) response criteria by visit. The LLDAS incorporates multiple measures of disease activity, specifically: (1) SLEDAI-2K ≤4, with no activity in major organ systems (renal, CNS, cardiopulmonary, vasculitis, fever) and no hemolytic anemia or gastrointestinal activity; (2) no new features of lupus disease activity compared with the previous assessment; (3) PGA (scale 0-3), ≤1; (4) current prednisolone (or equivalent) dose ≤7.5 mg daily; and (5) well tolerated standard maintenance doses of immunosuppressive drugs and approved biological agents, excluding investigational drugs.
	Proportion of participants with a state of disease control, defined as a SLEDAI-2K score ≤2, achieved without immunosuppressants and with

Objectives	Endpoints
	corticosteroids at a prednisone equivalent dose of ≤5 mg/day, by visit; using the Principal Investigators assessment of SLEDAI-2K. • Proportion of participants with a state of clinical remission, defined as a Clinical SLEDAI-2K score =0, achieved without immunosuppressants and with corticosteroids at a prednisone equivalent dose of 0 mg/day, by visit; using the Principal Investigators assessment of SLEDAI-2K. (Serological activity score, i.e. anti-dsDNA positivity and/or hypocomplementemia, is excluded from the Clinical SLEDAI-2K endpoint.)
Secondary: Safety	
To assess the safety and tolerability of belimumab and a single cycle of rituximab administered in a combination regimen to adult participants with SLE	Incidence of adverse events (AEs) including serious AEs (SAEs) and AEs of special interest (AESIs)

Objectives	Endpoints
Secondary: Patient Reported Outcomes (PROs)	
To assess the impact of belimumab and a single cycle of rituximab administered in a combination regimen to adult participants with SLE on PROs	 Change from baseline in Patient Global Assessment (PtGA) by visit Change from baseline in LupusQoL domain summary scores (8 domains) by visit Change from baseline in FACIT-Fatigue score by visit Proportion of subjects with improvement in FACIT-Fatigue score exceeding the Minimal Clinically Important Difference (MCID, ≥4) by visit
Exploratory: Pharmacokinetics and Biomarkers	
To assess pharmacokinetics of and biomarker response to belimumab and a single cycle of rituximab administered in a combination regimen to adult participants with SLE	 Belimumab and rituximab concentrations by visit Change from baseline in autoantibodies by visit Change from baseline in peripheral blood leukocytes including B cell subsets by visit Change in BLyS levels from baseline by visit
Exploratory: Patient Reported Work Productivity	
To explore the impact of belimumab and a single cycle of rituximab administered in a combination regimen to adult participants with SLE on patient experience and productivity	 Change from baseline in Work Productivity and Activity Impairment (WPAI): Lupus percent overall work productivity impairment score by visit Change from baseline in WPAI: Lupus percent activity impairment score by visit

STUDY DESIGN

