2.1.4. Efficacy Tables

| Efficacy Tables | | | | |
|--------------------|-------------------|------------|--|---|
| New output number | Old output number | Population | Title | Major modifications since original RAP |
| Clinical Remission | | | | |
| 22.01. | 22.01 | MITT | Clinical Remission (IBA) at Week 64 (Hybrid) | |
| 22.02. | 22.02 | MITT | Logistic Regression Analysis of Clinical Remission (IBA) at Week 64 (Hybrid) | |
| 22.03. | 22.03 | MITT | Disposition of Clinical Remission (IBA) at Week 64 (Hybrid) | |
| 22.04. | NEW | MITT | Disposition of Clinical Remission (IBA) by First Reason for Non-Response at Week 64 (Hybrid) | 
 • New output (omission in original RAP) |

| Efficacy Tables | | | | |
|-------------------|-------------------|------------|---|---|
| New output number | Old output number | Population | Title | Major modifications since original RAP |
| 22.05. | 22.04 | MITT | Clinical Remission (IBA) and its Components at Week 64 (Hybrid) | 
 The planned component for 'Corticosteroid >0 to <=5mg/day' has been modified to match the actual component of the endpoint, i.e. "Corticosteroids at a prednisone equivalent dose of 0 mg/day" |
| 22.06. | NEW | MITT | Clinical Remission (IBA) and its Components by Baseline C3/C4 Level & Anti-dsDNA at Week 64 (Hybrid) | 
 New output (key subgroup of interest) The planned component for 'Corticosteroid >0 to <=5mg/day' has been modified to match the actual component of the endpoint, i.e. "Corticosteroids at a prednisone equivalent dose of 0 mg/day" |
| 22.07. | 22.08 | MITT | Clinical Remission (IBA) by Visit (Hybrid) (Year 2) | |
| 22.08. | 22.09 | MITT | Clinical Remission (PI) by Visit (Hybrid) (Year 2) | |
| 22.09. | 22.25 | MITT | Duration of Clinical Remission (PI) (Hybrid) (Year 1&2) | |
| 22.10. | 22.20 | MITT | Clinical Remission (PI) Sustained for at least 24 Weeks by Visit (Hybrid) (Year 2) | |
| 22.11. | 22.33 | MITT | Time to Clinical Remission (PI) Sustained for at least 24 weeks and maintained through to Week 104 [1] (Hybrid) | |
| Disease Control | | | | |
| 22.12. | 22.10 | MITT | Disease Control (IBA) at Week 104 (Hybrid) | |
| 22.13. | 22.11 | MITT | Logistic Regression Analysis of Disease Control (IBA) at Week 104 (Hybrid) | |
| 22.14. | 22.12 | MITT | Disposition of Disease Control (IBA) at Week 104 (Hybrid) | |

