| 22.15. | NEW | MITT | Disposition of Disease Control (IBA) by First Reason for Non-Response at Week 104 (Hybrid) | 
 New output (omission in original RAP) |

| Efficacy Tables | | | | |
|---|--------------------------|-------------------|--|--|
| New output number | Old output number | Population | Title | Major modifications since original RAP |
| 22.16. | 22.13 | MITT | Disease Control (IBA) and its Components at Week 104 (Hybrid) | |
| 22.17. | NEW | MITT | Disease Control (IBA) and its Components by Baseline C3/C4 Level & Anti-dsDNA at Week 104 (Hybrid) | 
 • New output (key subgroup of interest) |
| 22.18. | 22.17 | MITT | Disease Control (IBA) by Visit (Hybrid) (Year 1&2) | |
| 22.19. | 22.18 | MITT | Disease Control (PI) by Visit (Hybrid) (Year 1&2) | |
| 22.20. | NEW | MITT | Duration of Disease Control (PI) (Hybrid) (Year 1&2) | 
 • New output (omission in original RAP) |
| 22.21. | 22.24 | MITT | Time to Disease Control (PI) Sustained for at least 24 weeks and maintained through to Week 104 [1] (Hybrid) | |
| Complete Remission | | | | |
| 22.22. | 22.21 | MITT | Complete Remission (PI) by Visit (Hybrid) (Year 2) | |
| 22.23. | 22.19 | MITT | Complete Remission (PI) Sustained for at Least 24 Weeks by Visit (Hybrid) (Year 2) | |
| Flares | | | | |
| 22.24. | 22.22 | MITT | Time to First Severe Flare (Treatment Policy, TF=Severe Flare) (Year 1&2) (Modified SLE Flare Index) | |
| 22.25. | NEW | MITT | Time to First Severe Flare (Treatment Policy) (Year 1&2) (Modified SLE Flare Index) | 
 • New output (of interest following post SAC request for Year 1) • Treatment Failures are not included as severe flares |
| 22.26. | 22.23 | MITT | Time to First Flare (Treatment Policy, TF=Flare) (Year 1&2) (Modified SLE Flare Index) | |
| Systemic Lupus Erythematosus Disease Activity Index 2000 (SLEDAI-2K) | | | | |
| 22.27. | 22.26 | MITT | SLEDAI-2K (PI) - Change from Baseline by Visit (Hypothetical) (Year 1&2) | |

| Efficacy Tables | | | | |
|---|-------------------|------------|---|--|
| New output number | Old output number | Population | Title | Major modifications since original RAP |
| 22.28. | 22.27 | MITT | SLEDAI-2K (PI) - Organ System Improvement by Organ System and Visit Among Subjects with Organ System Involvement at Baseline [1] (Treatment Policy) (Year 1&2) | |

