7.7.5. Statistical Methodology Specification for Time to Event Endpoints

| |
|--|
| Endpoints |
| 
 Time to first severe flare (as measured by the modified SLE Flare Index) [T12.33, T22.22, F12.12,F22.06] |

- Time to first flare (as measured by the modified SLE Flare Index) [T12.34, T22.23,F12.09,F22.07]
- Time to disease control sustained to Week 104, defined as SLEDAI-2K score ≤ 2 (PI), achieved without immunosuppressants and with corticosteroids at a prednisone equivalent dose of ≤ 5 mg/day.[T22.24,F22.09].
- Time to clinical remission sustained to Week 104, defined as Clinical SLEDAI-2K score=0 (PI) (Section 15.6.3), achieved without immunosuppressants and with corticosteroids at a prednisone equivalent dose of 0 mg/day [T22.33].

Derivation

Flare Endpoints

| Subject | Time to defined as: | Censored |
|--|---|----------|
| Flare | Date of 1 st flare – trt start date +1 | No = 0 |
| TF before or without flare | Date of 1 st TF – trt start date +1 | No = 0 |
| Subjects without a Flare or TF who have an intercurrent event: | | |
| Withdraw | Date of last Flare assessment prior to intercurrent event – trt start date +1 | Yes =1 |
| Lost to Follow-up | | |
| Die | Date of Death – trt start date +1 | Yes =1 |
| For Year 1 reporting: | | |
| Subject completes Week 52 | Date of Week 52 visit – trt start date +1 | Yes =1 |
| For Year 2 reporting: | | |
| Subject completes Week 104 | Date of Week 104 visit – trt start date +1 | Yes =1 |

- The flare criteria will be programmed from the SLEDAI-2K irrespective of data recorded on the SFI form
- Flares recorded as severe on the SFI form will be downgraded to not severe in the programmed endpoint if the only cause of the severe flare was SLEDAI-2K>12
- Only post baseline flares will be included in the analysis (Flares on Day 1 will not be considered)
- Treatment failure is considered as a severe flare.
- Subjects who do not have a flare assessment post baseline will be censored at Day 1 and hence reported as 'time to' defined as 1 and censor =Yes = 1

Time to Response Endpoints

| Subject | Time to defined as: | Censored |
|---------------------------------------|--|----------|
| Sustained response | Date of 1 st sustained response – trt start date +1 | No = 0 |
| | | |
| Subjects without a sustained response | | |

| | | |
|--|--|--------|
| Withdraw | Date of last visit prior to intercurrent event – trt start date +1 | Yes =1 |
| Lost to Follow-up | | |

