| 
A subject has a sustained disease control at a visit if all of the following criteria are met:
 
 1 In disease control at the visit 2 In disease control at the first visit that is at least 24 study weeks prior, or if disease control cannot be assessed at that visit, then in disease control at the visit prior. 3 In disease control for all assessed visits between (1) and (2). Note assessments can be missing. 
Note: 24 weeks refers to the difference in visit ‘labels’ not calendar weeks between visits. The first visit of sustained disease control is defined as the 1st visit that the subject is a disease control responder and all subsequent visits up to and including Week 104 the subjects is also a disease control responder. Missing assessments are not considered.
 
Time to disease control sustained to Week 104 = 1st visit of sustained disease control - treatment start date (Day 1) +1
 |
| 
Duration of Disease Control
 |
| 
The duration of disease control is defined as the longest period between 2 visits that the subject is a disease control responder at all visits. Missing assessments are not considered. Duration of disease control = longest period where 1st visit of disease control – last visit of disease control + 1
 |

| Example Subject | SLEDAI-2K score at Week 52 | Study Withdrawal (including Lost to Follow-up, or Death) prior to Week 52 | Treatment Failure prior to Week 52 | IP Discontinuation prior to Week 52 | Main Estimand (Hybrid) | Supportive Estimand (Composite) | (Hybrid On Treatment) | Treatment Policy |
|-----------------|---|---|------------------------------------|-------------------------------------|------------------------|---------------------------------|-----------------------|------------------|
| 1 | >2 | N | N | N | NR | NR | NR | NR |
| 2 | >2 | N | N | Y | NR | NR | Excluded | NR |
| 3 | >2 | N | Y | N | NR | NR | NR | NR |
| 4 | >2 | N | Y and prior to IP discontinuation | Y | NR | NR | NR | NR |
| 5 | >2 | N | Y but post IP discontinuation | Y | NR | NR | Excluded | NR |
| 6 | <=2 | N | N | N | R | R | R | R |
| 7 | <=2 | N | N | Y | R | NR | Excluded | R |
| 8 | <=2 | N | Y | N | NR | NR | NR | R |
| 9 | <=2 | N | Y and prior to IP discontinuation | Y | NR | NR | NR | R |
| 10 | <=2 | N | Y but post IP discontinuation | Y | NR | NR | Excluded | R |
| 11 | Incomplete* or entirely missing | N | N | N | NR | NR | NR | NR |

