| 
Clinical Remission Sustained For At Least 24 Weeks
 
Sustained response will be reported for all weeks post Week 52 (Year 2), and at any timepoint (i.e. any subjects who had a sustained response at any time during Year 2). Statistical analysis will only be conducted at Week 104 and at ‘any timepoint’.
 
A subject has a sustained remission at a visit if all of the following criteria are met:
 
 1 In clinical remission at the visit 2 In clinical remission at the first visit at least 24 study weeks prior, or if clinical remission cannot be assessed at that visit, then in clinical remission at the visit prior. 3 In clinical remission for all assessed visits between (1) and (2). – Note assessments can be missing. 
Note: 24 weeks refers to the difference in visit ‘labels’ not calendar weeks between visits.
 |

[figure not shown]
| |
|--|
| Time to Clinical Remission Sustained to Week 104 |
| The first visit of sustained clinical remission is defined as the 1 st visit that the subject is a clinical remission responder and all subsequent visits up to and including Week 104 the subjects is also a clinical remission responder. Missing assessments are not considered (the rules for sustained response for at least 24 weeks as defined above are also applied here). |
| Time to clinical remission sustained to Week 104 = 1 st visit of sustained clinical remission - treatment start date (Day 1) +1 |
| Duration of Clinical Remission |
| The duration of clinical remission is defined as the longest period between 2 visits that the subject is a clinical remission responder at all visits. Missing assessments are not considered Duration of clinical remission = longest period where 1 st visit of clinical remission – last visit of clinical remission + 1 |

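### The RAP adds a 24-week minimum to two time-to-event endpoints that the protocol defines only as sustained to Week 104, and does not list this as a change

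*Protocol*

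**What the plan says.** **Protocol.** Section 4 lists two time-to-event endpoints among the other secondary efficacy endpoints: "Time to disease control sustained to Week 104, defined as SLEDAI-2K score ≤2, achieved without immunosuppressants" and "Time to clinical remission sustained to Week 104, defined as Clinical SLEDAI-2K score =0, achieved without immunosuppressants", each with its corticosteroid limit. Neither has a minimum length of response, and the synopsis agrees. The same list uses a 24-week minimum for different endpoints, namely the proportions with complete remission and with clinical remission.

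**RAP, endpoint lists.** RAP 2.2 and 7.7.5 keep the protocol form. For example, 7.7.5 has "Time to disease control sustained to Week 104, defined as SLEDAI-2K score" and continues without a minimum.

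**RAP 15.6.4, time to disease control.** The entry first gives criteria for being sustained at a visit. One of them is "In disease control at the first visit that is at least 24 study weeks prior", counted by visit label and not by calendar time. It then defines the first visit of sustained control as the first responder visit for which at "all subsequent visits up to and including Week 104 the subjects is also a disease control responder". That second sentence has no minimum.

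**RAP 15.6.5, time to clinical remission.** It has the same first-visit sentence, and adds that "the rules for sustained response for at least 24 weeks as defined above are also applied here".

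**RAP Addendum 2, Section 2.1.4.** Table 22.21 is titled "Time to Disease Control (PI) Sustained for at least 24 weeks and maintained through to Week 104" and Table 22.11 "Time to Clinical Remission (PI) Sustained for at least 24 weeks and maintained through to Week 104". The column for major modifications is blank for both.

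**RAP 2.1**, which covers changes to the protocol-defined analysis, does not mention the 24-week condition.

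**The concern.** The protocol treats response held to Week 104 and response held for at least 24 weeks as separate ideas and uses each for different endpoints. The RAP derivations combine them for the two time-to-event endpoints, while the RAP's own endpoint lists do not. A response that begins late in Year 2 and is still present at Week 104 meets the protocol wording but fails the derivation.

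At stake are the event counts, the event-time summaries and the Cox hazard ratios in Tables 22.11 and 22.21. A reader who looks for the protocol endpoint in the final report would find only the narrower version, with no statement that it departs from the protocol. For disease control there is a second problem: RAP 15.6.4 sets the two rules next to each other without saying how they combine, so two programmers could derive different datasets from the same text.

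**Working it through.** The plan gives no figure to reproduce, so the check is to apply each rule to the visit schedule.

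**Inputs**
- Post-baseline investigator SLEDAI-2K visits (Schedule of Activities, Year 1 and Year 2): Weeks 4, 8, 12, 16, 20, 24, 26, 28, 32, 36, 40, 44, 48, 52, 60, 64, 72, 80, 88, 96 and 104, which is 21 visits.
- Rule A (protocol, RAP 7.7.5, second sentence of RAP 15.6.4): response at every assessed visit from the start of the run to Week 104.
- Rule B (24-week criteria): response at Week 104, at the nearest visit at least 24 weeks earlier by label, and at all assessed visits between.
- Censoring (RAP 7.7.5): completers without a sustained response or treatment failure are censored at the Week 104 visit.

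**Cut-off.** 104 − 24 = 80. With all visits assessed, the latest start that satisfies rule B at Week 104 is Week 80.

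| Start of final run | Rule A | Rule B at Week 104 | First visit that meets the 24-week criteria |
|---|---|---|---|
| Week 52 | event, Week 52 | met | Week 80 |
| Week 60 | event, Week 60 | met | Week 88 |
| Week 64 | event, Week 64 | met | Week 88 |
| Week 72 | event, Week 72 | met | Week 96 |
| Week 80 | event, Week 80 | met | Week 104 |
| Week 88 | event, Week 88 | censored, Week 104 | none |
| Week 96 | event, Week 96 | censored, Week 104 | none |
| Week 104 | event, Week 104 | censored, Week 104 | none |

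So 3 of the 21 possible start visits change status.

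**Missed visits.** If Week 80 is not assessable, rule B falls back to Week 72, and a Week 88 start still fails. If Week 104 is not assessed and the rule is applied at Week 96, then 96 − 24 = 72, and a run starting at Week 80 fails as well.

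**Where the two versions can differ.** If both versions date the event at the start of the run, and all visits are assessed, every event up to Week 80 has the same date and the same risk set under either rule. The affected participants remain at risk for 104 − 88 = 16, 104 − 96 = 8 or 0 further weeks under rule B. The Kaplan-Meier curves therefore separate only from Week 88, and a percentile reached by Week 80 does not move. What changes is the number of events, the late contribution to the hazard ratio, and the summary of study day among participants with an event.

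**Event date in RAP 15.6.4.** If the event were instead dated when the criteria are first met (last column), a Week 64 start would become a Week 88 event and the whole curve would shift. The time formula in both sections uses the first visit of the run, which favours the start date. Only RAP 15.6.5 also says that both sets of rules apply.

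**The case against.** The strongest reply is that an endpoint described as sustained needs an operating rule: without a minimum, a single response seen only at Week 104 counts. The protocol leaves the other secondary efficacy analyses to the RAP (Section 10.4.3). The 24-week rule is in the RAP of 5 August 2020, and Addendum 1 of 8 October 2020 still predates database release, so the rule is prespecified and not driven by results. The Addendum 2 titles disclose it. All of this stands, and it is why the 24-week analysis should be kept. It does not make that analysis the protocol's endpoint, and it does not remove the need to list the departure.

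A reader might also infer more than the documents support:
- That Addendum 2 contradicts itself. It does not: its titles join the two conditions, and it holds no event definition of its own. The text of the footnote marked in both titles is not available.
- That RAP 15.6.5 is equally unclear. It states that both rules apply.
- That anyone in response at Week 88 or later is affected. Only a final run that starts then is affected; a run that began at Week 40 and includes Week 88 is an event either way.
- That half of clinical remission events are lost. The recommended taper from 5 mg takes 35 weeks, and 26 + 35 = Week 61. That leaves Weeks 64, 72, 80, 88, 96 and 104 as start visits, of which 3 of 6 fail. But this follows one taper path, participants may enter on no corticosteroid, and visits are not events unless starts are assumed to be evenly spread.
- That the two candidate dates differ by at least 168 days. 24 × 7 = 168 is a difference in visit labels. With ±7-day windows the gap can be 168 − 14 = 154 days, and with the ±28-day COVID-19 windows 168 − 56 = 112.

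**Conclusion.** The mismatch is real for both endpoints. The protocol and the RAP's endpoint lists set no minimum duration; the RAP derivations and the Addendum 2 titles set 24 weeks; and RAP 2.1 does not record the change. Among participants without treatment failure or withdrawal, a final unbroken run that starts at Week 88, 96 or 104 moves from event to censored. That is 3 of 21 post-baseline investigator visits, assuming that all visits are assessed and that weeks are counted by label. The number of participants involved, and the effect on the hazard ratios, cannot be derived from the documents. The lack of a rule for combining the two definitions is confined to RAP 15.6.4.

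The consequence is limited. These are other secondary endpoints outside the step-down testing sequence (RAP 5.6), so the primary and major secondary conclusions do not depend on them. The correction is still worth making, because two named protocol endpoints would otherwise be reported only in a narrower form.

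**What to change.** - In RAP 15.6.4 and 15.6.5, set the event date to the first visit of the unbroken run of response that reaches Week 104.
- Report the protocol definition, with no minimum duration, under the protocol's endpoint name.
- Keep the prespecified 24-week version as a separately labelled analysis, also dated at the start of the run, and title the tables so that the two cannot be confused.
- List the 24-week condition as a departure from the protocol wording, in RAP 2.1 or in an addendum.

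The cost is RAP wording, table titles and one extra run of existing code. No new data are needed.
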